
Brain Response to Baclofen versus Placebo during Smoking Cue Exposure

The phenomenon of brain and behavioral drug cue reactivity is complex and multifaceted. As we have shown previously, genetic variance, sex, hormones, and many other variables affect smoking cue reactivity. As such, we cannot expect that one medication will be helpful in every individual, which is why one goal of our GABA B R01 grant was to identify a cue-vulnerable baclofen-responsive endophenotype. In spite of the multitude of inter-individual differences that can provide protection or confer vulnerability to smoking reminders, we were able to show an overall reduction in smoking cue reactivity in baclofen-treated subjects that was not observed in placebo-treated subjects (N = 22 per group). The figure (right) shows reduced brain activity during smoking cue versus nonsmoking cue exposure in individuals receiving 20 mg baclofen, q.i.d. Similar to our study in cocaine patients during cocaine cue exposure (Young et al, *J. Neuroscience*, 2014), baclofen blunted smoking cue responses in the medial orbitofrontal cortex, ventral medial prefrontal cortex and bilateral anterior ventral insula (i.e., mesolimbic circuitry). This study adds to the literature by comparing brain activity before and during treatment, and by examining baclofen's effects in nicotine use disorder (NUD). There were no differences in smoking cue neural reactivity between pre- and during treatment comparisons in the placebo group. This data is currently being prepared for dissemination to the scientific community.

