Pharmacogenetics is a promising and novel addition to neuroimaging studies. Twin, family and adoption studies indicate that vulnerability to substance abuse is partially inherited. Individual response to medications will most likely be related to genetic phenotypes. Genetics studies, on their own, require huge sample sizes and are expensive; however, when combined with neuroimaging, which offers a 'picture' of individual brains, we can learn why some individuals respond to a particular medication and others do not. For example, evidence suggests that the rewarding properties of drugs involve activation of the mesocorticolimbic dopaminergic system, and thus, dopaminergic genes will be examined. Candidate dopamine genes include DRD1, DRD2, DRD3, DRD4, DRD5, COMT and DAT. In addition, is also evidence that GABA-ergic mechanisms are involved, particularly the GABA B2 subunit. Therefore, we will examine it as well. The most compelling evidence for a role for variance in dopaminergic components in smoking cue reactivity exists for the dopamine transporter (DAT). Thus, the DAT gene will be our primary focus. The DAT gene has two common polymorphisms. One is the 9 variable number tandem repeat (VNTR) allele and the other is the 10 VNTR allele. Those with the strongest smoking cue responses have at least one 9 VNTR (hetero- or homozygotes) while reduced smoking cue responses occur in those homozygous for the 10 VNTR allele.

OBJECTIVES

1. Overall Objectives

AIM 1 Compare brain and behavioral measures in subjects who are carriers of a dopamine transporter (DAT) 9 (VNTR: 9-repeats) versus 10 VNTR homozygotes (10/10-repeats), actively seeking smoking cessation treatment.

Hypothesis: We will replicate our original findings of differential brain and behavioral responses to cues mediated by variance in the DAT gene. Brain activity will be enhanced in the interconnected ventral striatum and medial orbitofrontal cortex, regions involved in conditioned drug reward, in 9-repeats compared to 10/10-repeats. Brain and behavioral responses will be significantly greater in 9-repeats compared to 10/10-repeats.

AIM 2. Compare brain and behavioral measures following 3 weeks of baclofen versus placebo treatment in treatment seeking subjects.

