*Part of the physical ** Part of the Psych Eval *** Collected pre- and post scan ⁺ Occurs the same day as the Quit Wk appt

2. Analyses

Imaging Data Processing: Prior to performing analyses, brain data are examined for gross movement and full image acquisition. An SPM-based ASL data processing toolbox is used for data analyses. ASL image pairs are realigned to the mean of all control images and spatially smoothed with a 3D isotropic Gaussian kernel with FWHM of 10mm. CBF image series are generated using a simplified two-compartment model with the sinc interpolation method for CBF calculations. The mean control image of each subject's data is co-registered to a HR 3D T1 structural image using the mutual information based co-registration algorithm provided by SPM8. The same co-registration parameters are used to co-register the CBF maps to the structural image. The structural image is then spatially normalized to the MNI standard brain. The same parameters are used to normalize the CBF images to the MNI standard space. Each subject's normalized mean control images are segmented using SPM8. The segmented gray matter masks are averaged and the overlap of subject's gray matter is extracted. This final mask is used for calculating global CBF for each session.

Imaging Data Analyses: Voxel-wise analyses of the CBF data are conducted on each subject using a general linear model (GLM). Global CBF time course is included in the model as a covariate to examine the effects of baclofen. Analyses are conducted on absolute (RB) and relative (during SC exposure) CBF. No temporal smoothing is applied. Contrasts between conditions (Time 1 versus Time 2) are defined in the GLM model to assess the voxel by voxel CBF difference. Using the corresponding parametric maps of this contrast (maps), random effects analysis is employed to test for a significant main effect of condition with a SPM map of the T statistic at each voxel for population inference for each session for the placebo and baclofen groups (second-level analysis). A 2x2 factorial design matrix is used to assess the effects of the pharmacological manipulation by including the group (baclofen vs placebo) and condition (Time 1 vs Time 2) as the two factors. This two-stage analysis is theoretically equivalent to a 2 way ANOVA.

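### The closing results summary credits baclofen with reducing cue reactivity on two within-arm findings and cites no between-arm contrast, although the plan already has a group by time model for it

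*Combined protocol and SAP*

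**What the plan says.** Aim 2 (Overall Objectives) is a between-arm question: "Compare brain and behavioral measures following 3 weeks of baclofen versus placebo treatment in treatment seeking subjects".

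Imaging Data Analyses, in the Analyses section, plans a suitable model: "A 2x2 factorial design matrix is used to assess the effects of the pharmacological manipulation by including the group (baclofen vs placebo") with Time 1 versus Time 2 as the second factor, described as equivalent to a two-way ANOVA. The same paragraph also plans tests of condition within each arm, "for population inference for each session for the placebo and baclofen groups (second-level analysis"). It does not name the interaction as the drug term and states no imaging threshold. The .05 level appears under Behavioral Analyses.

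The section titled Brain Response to Baclofen versus Placebo during Smoking Cue Exposure, placed after the references, reports an "overall reduction in smoking cue reactivity in baclofen-treated subjects that was not observed in placebo-treated subjects (N = 22 per group"). On placebo it says: "There were no differences in smoking cue neural reactivity between pre- and during treatment comparisons in the placebo group". The figure is described in terms of baclofen subjects: "The figure (right) shows reduced brain activity during smoking cue versus nonsmoking cue exposure in individuals receiving 20 mg baclofen, q.i.d". The contribution claimed is a before/during one: "This study adds to the literature by comparing brain activity before and during treatment". The section concludes that baclofen dampened responses in named mesolimbic regions, and adds: "This data is currently being prepared for dissemination to the scientific community".

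**The concern.** A change that passes a threshold in one arm and fails to pass it in the other is not a test of whether the arms differ. The difference between a significant and a non-significant result may itself be small and imprecise. The quantity Aim 2 needs is the difference between the two changes, which is the group by time term of the planned 2x2.

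The summary's heading and conclusion are comparative and causal, while the evidence in its text is two separate before/during comparisons. This is the only Aim 2 imaging conclusion reported in the documents, and it was heading for publication. If the between-arm contrast is weak or was not run, readers would take a change on baclofen as an established drug effect.

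**Working it through.** **What can be reproduced.** The summary gives a count (22 per group) but no mean change, SD, test statistic, p-value or interval, so its result cannot be recomputed. The effect sizes in the sample size section (0.78 and 0.98) are for DAT genotype, not drug, and cannot stand in. What follows shows only what the stated pattern can and cannot imply.

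**Inputs.** From the documents: n = 22 per arm. Assumed: one region, equal SD of change in both arms, and two-sided thresholds of .05, .01 and .001. Reductions are positive and in SD units of change.

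**Step 1. Smallest baclofen reduction that is significant within the arm.** d = t(1−α/2, 21 df)/√22:
- .05: 2.080/4.690 = 0.443
- .01: 2.831/4.690 = 0.604
- .001: 3.819/4.690 = 0.814

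**Step 2. Between-arm test of that result.** t = (d − placebo change)/√(2/22), where √(2/22) = 0.3015, on 42 df.

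| Baclofen just reaches | Placebo change 0: t, p | Placebo falls 0.2 SD: p | Placebo rises 0.2 SD: p |
|---|---|---|---|
| .05 | 1.47, 0.149 | 0.42 | 0.039 |
| .01 | 2.00, 0.052 | 0.19 | 0.011 |
| .001 | 2.70, 0.010 | 0.048 | 0.0016 |

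A placebo change of 0.2 SD either way has t = 0.2 × 4.690 = 0.94 and p = 0.36 within its own arm, so it could be reported as no difference.

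**Step 3. Interval.** The 95% half-width is t(.975, 42) × 0.3015 = 2.018 × 0.3015 = 0.61 SD. With zero placebo change the differences are 0.44 (−0.17 to 1.05), 0.60 (−0.005 to 1.21) and 0.81 (0.21 to 1.42).

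**Step 4. What the baclofen result would have to be.** With zero placebo change, the between-arm test passes the same threshold only if the baclofen p-value is below about .0095, .0010 or .00006 respectively.

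**Step 5. Unequal SDs.** If the placebo SD is half or twice the baclofen SD (Welch, 30.9 df), the zero-placebo-change p-values become 0.07 or 0.36 at .05, 0.02 or 0.21 at .01, and 0.002 or 0.10 at .001.

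**Step 6. How often the pattern arises with no drug effect.** Rate = P(baclofen shows a significant reduction) × P(placebo not significant), from the noncentral t with the same true change in both arms. At .05:
- Common change 0: 0.025 × 0.95 = 0.024, which is no inflation over the directional between-arm rate of 0.025.
- Common change 0.2 SD: 0.144 × 0.855 = 0.123.
- Common change 0.45 SD: 0.521 × 0.479 = 0.250.
- Common change 0.5 SD: 0.609 × 0.391 = 0.238.

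The range of 12–25% therefore applies only if both arms share a true change of 0.2–0.5 SD.

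**Step 7. Allocation.** The Randomization paragraph gives 2:1. For 44 subjects that means 44 × 2/3 = 29.3 and 44/3 = 14.7, about 29 v 15 rather than 22 v 22.

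**The case against.** **The plan is sound and this is only a summary.** Largely right. The planned 2x2 is stated to assess the drug, and with those two factors the interaction is its natural reading. A reader might infer that the trial plans the wrong analysis; the documents do not support that. The fault lies in the inference stated in the summary, and the change to the analysis section is a clarification.

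**The figure is missing.** Also right. A contrast label or threshold may sit there, and the contrast may have been run. A reader might infer that no between-arm test was done or that baclofen had no effect; neither follows. What stands is that the prose describes the figure as showing baclofen subjects and cites only within-arm evidence.

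**The magnitudes are assumed.** They are. A placebo rise favours the drug: at the .05 row, a 0.2 SD rise brings the between-arm p to 0.039. At the .001 row with zero placebo change, the interval already excludes zero. With a pooled test and a placebo SD below about 0.25 / 0.32 / 0.41 of the baclofen SD, a baclofen result that just passes .05 / .01 / .001 would also pass between arms. So the pattern does not always fail between arms.

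**The false-pattern rates need a common change.** Correct. None is documented, the cue sets are counterbalanced against habituation, and the perfusion method is described as stable over time. Those rates also treat one region and one test, whereas the summary describes several regions. A reader might take 12–25% as this trial's error rate; the documents do not support that.

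**Conclusion.** The point holds as one about stated evidence. The summary's text supports a before/during change on baclofen; it does not establish a baclofen-versus-placebo difference. Depending on an unreported placebo change of only 0.2 SD in either direction, a baclofen result at the .05 margin corresponds to a between-arm p anywhere from 0.039 to 0.42. At the .001 margin the range is 0.0016 to 0.048. These figures assume 22 v 22, equal SDs of change and a single region, because the documents give no change, SD or imaging threshold.

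The 22 per group does not match 2:1 allocation, and the text does not explain it. A reader might infer selective inclusion; the documents do not say how the 44 were chosen, so only an explanation can be asked for.

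This should be corrected before the result is disseminated. It does not call the design or the planned model into question.

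**What to change.** 1. In the closing summary, rest the conclusion on the planned group by time contrast. Give its estimate, 95% CI and threshold, in all randomised subjects with two usable scans at their actual allocation. If the contrast has been run, report it. If it cannot be given, describe the result as a change within the baclofen arm.
2. State how 22 per group arose under 2:1 randomisation.
3. As a clarification, add a sentence to Imaging Data Analyses naming the group by time interaction as the test of the Aim 2 drug effect.

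Cost: one contrast on existing maps (or reporting one already run), one sentence in the plan, and rewording. No new data are needed. The claim may become weaker: the 95% half-width is about 0.61 SD of change at 22 v 22. If the 85 subjects expected after attrition (100 − 15) were all analysed at 2:1, about 57 v 28, it would be 1.989 × √(1/57 + 1/28) = 1.989 × 0.231 = 0.46 SD.
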